1.4 REFERRALS	
Has the Project been referred to BSREC from another REC or delegated process?	Yes  No 
If yes, please provide the reason:	

Referred by HSSREC as project involves the NHS	
Referred by department as not within the remit for delegated approval	
Other	
Please provide details:	

SECTION 2. PROJECT DETAILS

2.1 Project Title:	Influenza 2020/2021
2.2 Estimated start date:	15/09/2020
2.3 Estimated completion date of project:	01/09/2021
2.4 Does the project involve the NHS or social care:	Yes:  No: 
2.5 Type of Project: https://warwick.ac.uk/services/ris/research_integrity/researchethicscommittees/biomed/study_design/ Research  NHS Service evaluation or Development  NHS Clinical Audit  Other- please specify:	
2.6 Research Sponsor: If not research in the NHS , please state N/A	N/A
2.7 Funder: If unfunded, please state N/A	N/A
2.8 IDEATE/Funder reference (if applicable) If your study is funded, please provide a reference	N/A
2.9 Links with other BSREC applications Is the project linked to any other BSREC application? If yes: Project title: Chief Investigator: BSREC Reference (if known): Nature of linkage:	Yes:  No: 

SECTION 3: BACKGROUND/LAY SUMMARY

Please provide a lay summary of the project:

The summary should be easily understood by someone who is not an expert in the area. Definitions and explanation of terms should be provided (avoid technical language).

To include:

- context for the proposed study
- a brief literature review supported by appropriate references
- a description of the proposed study and population to be studied building on review of previous studies/evidence
- the scientific benefit of the proposed study

As part of the fight against COVID-19, the UK government has announced its most comprehensive flu campaign to date (<https://www.gov.uk/government/news/most-comprehensive-flu-programme-in-uk-history-will-be-rolled-out-this-winter>). This should not be surprising, as every year NHS hospitals experience an overwhelming number of influenza cases, and COVID-19 increases this concern. As in previous years, the flu vaccine is free at the point of care for people 65 and over. New this year is that later in the season the vaccine will be made available free at the point of care for people 50 and over. However, if people refuse to take the vaccine this comprehensive program cannot benefit public health.

While access to vaccines remains a barrier to eradicating vaccine preventable disease in lower income countries, in higher income countries like the UK vaccine hesitancy stands in the way. In 2019, the World Health Organisation (WHO) listed increasing vaccine hesitancy as one of the ten biggest threats to global health. Recent outbreaks of vaccine preventable diseases, like measles and pertussis, are alarming. (Hotez, 2019). Over half of UK residents express vaccine hesitant attitudes (Luyten J, 2019), and a substantial proportion, 16%, already say they would refuse a COVID-19 vaccine. (<https://www.theguardian.com/media/2020/jul/07/almost-one-in-six-britons-say-would-refuse-covid-19-vaccine>; also see this report where only 53% of people are certain or very certain they would take up a COVID-19 vaccination when one becomes available: <https://www.kcl.ac.uk/news/whos-most-likely-to-refuse-a-covid-19-vaccine>).

The degree to which hesitancy is expressed varies across characteristics of the vaccine considered and the time and place it is offered, and across characteristics of the person including their perceptions of complacency, convenience, confidence, calculations, and communal responsibility, i.e. the “5Cs” (Betsch et al 2018). Information campaigns can be used to influence all the 5Cs, and public facing information is often a necessary component of public health campaigns that may also include structural components, i.e. complex interventions (Craig et al 2008). Largely, information campaigns can be viewed as a type of educational intervention.



SECTION 4 RISK ASSESSMENT AND ETHICAL CONSIDERATIONS CHECKLIST

Complete the checklist ticking 'Yes' or 'No' to all questions.

Where you have ticked 'Yes' to a question below, you will need to specifically address the ethical issues raised by that point and detail what safeguards will be put in place to minimise the potential risks/harm in the relevant section of the application form or in the space provided.

		Yes	No
A	Does the study involve participants who are particularly vulnerable or unable to give informed consent or in a dependent position (e.g. children, your own students, over-researched groups, people with learning difficulties, people with mental health problems, young offenders, people in care facilities, prisoners)? (If yes, please provide details in section 7 – Informed Consent)		

B	
Will participants be taking part in the study without their consent or knowledge at the time, or will deception of any sort be involved (e.g. covert observation of people in non-public places)?
 
(If yes, please provide details in section 7 – Informed Consent)
		
C	
Is there a risk that the highly sensitive nature of the subject might lead to disclosures from the participant concerning their involvement in illegal activities or other activities that represent a threat to themselves or others (e.g. sexual activity, drug use, or professional misconduct)?
 
If yes, please provide details:
		
D	
Could the study induce psychological distress or anxiety, or produce humiliation, or cause harm, or lead to negative consequences beyond the risks encountered in normal life?
 
 • Applicable to studies involving sensitive topics, vulnerable participants as well as studies involving driving experiments, simulators, computational or physiological experiments. For the latter, please detail potential risks associated with any equipment and how these will be monitored and addressed in the space below. • Please also consider the risk to individuals if any personally identifiable data collected as part of the study is accidentally disclosed. Please see guidance note for more information. 
If yes, please provide details:
 
The survey contains statements about political positions that participants may disagree with and experience strong feelings from considering. Including these statements is important to capture participants' political orientations the day they take the survey. In addition, the survey also contains statements about intentions to practice different health behaviours: receiving an influenza vaccination, receiving a future COVID-19 vaccination and wearing a mask. For each statement participants are explicitly asked to express how much they agree or disagree on a 7-point scale.
 
We want participants to (1) be able to freely choose whether to engage with the questions, (2) know that these questions are being asked for the purpose of research and that we are not advertising a particular view, and (3) feel comfortable expressing agreements and disagreements.
 
In the information sheet we now state the survey topics precisely to facilitate a more informed choice about whether to take part:
 
“If you choose to take part, the survey may take 8 minutes to complete. In it, you will be asked to answer questions about your health behaviours (taking up vaccines and wearing a mask) and background characteristics (including your political views, age and gender). You will be given some information about being vaccinated for influenza.
 
We plan to recruit 200 participants. There are no major foreseen personal risks or benefits, although some questions on politics or health may inspire strong feelings.”
 
We also emphasise that these are research questions that they can disagree with:
 
“The views expressed in the survey are not the views of the researchers or the University, but are here to allow participants like you to express their own views. You may not agree with some of the statements and are free to express disagreements.”
 
If participants do not want to answer questions about politics, they can withdraw from the survey by closing their browser window with no consequence. This is also stated in the information sheet:
 
“Can I withdraw? While taking the survey, you can withdraw at any time, and for
		

	
any reason, simply by closing your browser.”
 
Lastly, to take part in the survey participants will have to respond “YES” to a consent item that reads:
 
“I recognise that the views expressed in the survey are not the views of the researchers or the University, but are here to allow participants to express their own views, and that I am free to express disagreements.” This additional step helps to ensure that participants are actively engaging with this information.
		
E	
Does the study involve substantial physical exertion?
 
If yes, please provide details:
		
F	
Does the study involve the administration of any substance?
 
If yes, please provide details:
		
G	
Does the study involve physically intrusive procedures, use of bodily materials or human tissue, or DNA/RNA analysis?
 
 • Approval from the University’s GMBSC (Genetic Modification and Biosafety Committee) is required before collection or use of any of these materials within the United Kingdom. • For studies overseas, please consult the GMBSC to confirm that the require risk assessments are completed. 
If yes, please provide details: Click here to enter text.
		
H	
Is any reward, apart from travelling and other expenses, to be given to participants?
 
If yes, please provide details and justification for this, to ensure this is appropriate, and not seen as a bribe or to coerce participants into taking part:
		
I	
Could the proposal give rise to researchers having any conflicts of interest?
 
https://warwick.ac.uk/services/finance/resources/regulations/fp1
 
 • Consider relationships/previous personal interactions with participating organisations, participants etc. 
If yes, please provide details including how this will be managed:
		
J	
Will any part of the project be undertaken overseas?
 
If yes, please state which Country/Countries, the locations at which the project will be undertaken, e.g. public place, school, company, hospital, University, researcher’s office, including the services of an overseas cloud hosting provider for storage or a market research company etc. and the local permissions in place for this (where required):
 
Please see University Guidance for data processing overseas: https://warwick.ac.uk/services/idc/dataprotection/internationaldatatransfers/
		
K	
Will the researchers go to any areas where their safety may be compromised?
 
If yes, please provide details, including what measures will be put in place to minimise risks and ensure the researcher’s safety. A risk assessment should be submitted with the application:
		
L	
Will pregnant women be participants in the study?
 
 • Please note, while you may not purposefully be recruiting pregnant women to the study, consider if any special measures would need to be put into place or if it is appropriate for these individuals to take part, e.g. safety risks 
If yes, please provide details:
		
M	
Will the study involve children under 5 years old?
		

	If yes, please provide details:		
N	Is the research commissioned by the military ?* If yes, please provide details:		
O	Is the research commissioned under an EU security call ?* If yes, please provide details:		
P	Does the research involve the acquisition of security clearances ?* If yes, please provide details:		
Q	Does the research concern terrorist or extreme groups ?* If yes, please provide details:		
R	Does the research involve an intervention ? 
 An “intervention” here is understood as a systematic controlled change of participant conditions, which could be psychological or physical. It can include but is not limited to changes in diet, activity, access to information, or use of certain products. If yes, please provide details: It is an online survey in which participants will be randomly allocated to one of two groups. Each group will read a different appeal to take up the influenza vaccination.		
S	Does the study involve any additional ethical considerations or risks to participants or the researcher that are not listed above? If yes, please provide details:		

* Please refer to the University webpages on [Prevent Duty](#)

SECTION 5: STUDY DESIGN, METHODOLOGY & ANALYSIS

5.1 Clearly state the research aim(s) of the project:

To include:

- a clear explanation and justification for the research question(s)/aim(s)

To explore whether a message aligned with the moral foundations that underlie a person's political ideology increase their willingness to take up the seasonal influenza vaccination.

5.2 What are the objective(s) for the project:

- Objectives are intermediate steps that will help you to meet your research aim(s)

The main objective is to compare how people with different political ideologies respond to an appeal to take up the seasonal influenza vaccination, when the appeal content is aligned (or unaligned) with the moral foundations underlying those political ideologies.

We also plan to describe the characteristics of people who have and have not already taken up the vaccination (e.g. age), and their intentions to take up related health behaviours: receiving a future COVID-19 vaccination and wearing a mask.

5.3 Study design and data collection methods:

To include:

- a clear description of the study design and data collection methods
- a suitable design should reflect the aim(s) of the study
- This may include ethnography/observations, interviews, focus groups, questionnaires, document analysis etc.
 - Ethnography/Observations**- what/who will be observed, by whom, for how long? What equipment (if any) will be used for recording etc.?
 - Interviews**- who is conducting the interviews, how, where and when- by telephone/in person/skype; will they be recorded- how? How long will they last? How will the interview guide be developed? etc.
 - Focus groups**- who is leading, how will they be organised, when and where will they take place, how will they be recorded? How long will they last? etc.
 - Questionnaires**- who has designed the questionnaire, who will distribute it, how long will it take to complete etc.

- **Document analysis**- what documents will be requested, where from, by whom, what permissions are in place for this etc.
- **Experimental** – what tests/lab work will be undertaken on participants, by whom, is specialist training required before undertaking?
- **Secondary analysis of previously collected data**- analysis of data that has been previously collected by a third party for research or other purposes, that is not publicly available e.g. healthcare, student, financial records. Please state whether the data set is identifiable or anonymised.

This is an observational study with a randomized sub-component for participants who have not already received the seasonal influenza vaccination this season.

The study will be conducted as an online, anonymous questionnaire.

The questionnaire has been designed by the current research team using a university approved Qualtrics account.

According to Qualtrics estimates, it may take participants 8 minutes to complete. The survey is designed to be anonymous, e.g. no IP information will be collected. There are places for participants to write free-text responses, and any identifiable information entered in free-text boxes will be redacted from our data-files, as described in section 8.10. A PDF copy of the full survey (information/consent sheet and all questions) is attached as a supporting document. The anonymous link to the survey is provided here: http://warwick.co1.qualtrics.com/jfe/form/SV_cUXTQ1rMOWJFq7j. Any responses recorded before the survey is disseminated (e.g. from reviewers of this ethics application) will not be analysed and will be deleted before the planned participant recruitment commences.

Each part of the survey is described below.

****Receiving informed consent:** Participants will read an information sheet and give their informed consent to take part in the study. The information sheet will include statements that "The views expressed in the survey are not the views of the researchers or the University, but are here to allow participants to express their own views. You may not agree with some of the statements and are free to express disagreements." Only participants who indicate meeting all the eligibility criteria and who consent to the survey will be allowed to advance.

****Demographics:** Participants will be asked their age in years (options: 50 to 99+ and prefer not to say), resident region of England (9 ONS regions: <https://www.ons.gov.uk/geography/regions>), gender identity (male, female, non-binary, other, and prefer not to say) and ethnicity (5 UK groups, and prefer not to say: <https://www.ethnicity-facts-figures.service.gov.uk/style-guide/ethnic-groups>).

****Political ideology:** Before completing a 10-item conservatism scale used in a similar study investigating the effect of messages on behaviour (Day et al 2014), participants will be reminded that "We are interested in your opinions on a variety of issues. The views expressed here are not the views of the researchers or the University, but are here to allow participants to express their own views. You are free to express agreements and disagreements. We appreciate your honest responses." The questionnaire includes two questions related to each of the five issues: one worded in conservative terms (e.g. The economic market will naturally correct itself), while the other liberal terms (e.g. The government must regulate the economy). Participants will be asked how much they disagree or agree with each statement on a seven point scale from 'strongly disagree' to 'strongly agree'. Then they will be asked to self-report their political orientation measured using a seven point scale, from very liberal to very conservative; this question will act as a face-validity check that should highly correlate with the conservatism scale.

****Vaccination against influenza in 20/21 season:** Next participants will be asked whether they received an influenza vaccination in the 20/21 season already (Yes or No).

--Participants who say "yes", will then be asked approximately when they received the vaccination (DD/MM/YYYY), where they received the vaccination (GP, pharmacy, other) and if they went with anyone to get their vaccination (no, a friend, a family member, or someone else). Lastly, they will be asked to describe why they took up the vaccination this year in a free-text box.

--Participants who say "no", will then be randomly allocated to view one of two appeals to take up the influenza vaccination. As in Kidwell et al.'s (2013) study, one appeal aligns with a conservative ideology and the other aligns with a liberal ideology. After reading these appeals, participants will be asked about their agreement with several statements on a seven point scale; these statements are manipulation checks to verify that the appeals evoke the immediately intended foundations. Then participants will be asked whether they intend to take up the influenza vaccination this seasons on a seven point scale, from 'strongly disagree' to 'strongly agree', and then be asked to explain their answer in a free-text box.

**Spill-over behaviours: Next all participants (those who vaccinated already and those who did not) will be asked about their intentions to take up a future COVID-19 vaccination when one becomes available, and their intentions to wear a face mask in a store that does not require face masks using the same seven point scale, from 'strongly disagree' to 'strongly agree'.

**Closing: Participants who have not already vaccinated will see debriefing information that reminds them that the study should not be construed as medical advice, and that they should speak to a medical professional if they are uncertain if they should take up the influenza vaccine. Hyperlinks are provided for participants to learn more about the study this study is based on and to learn more about the UK's influenza vaccinations policies this year. We also provide them with the opportunity to tell us anything else they think is relevant to the survey in a free-text box, or write "I prefer not to say". We have found this free-text box to be useful in previous surveys to source alternative explanations for our findings.

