5.4 Data Analysis

To include:

- *Specifically what data sets will be collected (name, date of birth, email address, ethnicity, health status, financial records, IP address etc.)*
- *whether this data will be collected directly from participants (e.g. via questionnaires/interviews) or indirectly, from a third party (previously collected data set) and how i.e. web form, online application, paper form*
- *Detail the analysis methods that will be undertaken e.g. content analysis, framework analysis, interpretative phenomenological analysis etc. and any statistical analyses.*
- *Describe how and by whom any data will be transcribed, coded, de-identified, stored, transferred, accessed, archived*
- *Any software used in the analysis should be specified and detailed how it will be used in the project*

The data will be collected directly from participant responses to the anonymous survey described above. No IP addresses will be collected. The data will be downloaded from Qualtrics into an SPSS file that is then stored in password protected files on the University of Warwick's servers.

The data will be analysed by [name] using SPSS. All of this software is provided by the University of Warwick.

As a reminder this is a pilot study and our analyses are designed to inform a future study, for which we will seek future ethical approval early in 2021.

The primary analysis will only include those participants who have not yet vaccinated. The primary analysis will be a multiple regression. Participants average political ideology scores to the conservatism scale will be mean-centred. Then Political ideology (continuous variable), Appeal type (nominal variable) and the interaction between Political ideology and Appeal type will be used to predict vaccination intentions (continuous variable). We anticipate finding an interaction effect ($\alpha < .05$).

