- *Will the sample size provide enough data to answer the research question?*
- *If sampling will be continued until saturation is reached, then this should be stated and linked to the research question*
- *Sampling strategy- is this random, snowball, purposive, convenience etc.*
- *What is the rationale for this- it should reflect the methodological framework for the study*

The proposed sample size is 200.

Rationale/Sufficient size: This is a pilot study. The sample size is informed by a previous study (Kidwell et al 2014, Study 1) where 82 participants took part. We are recruiting more participants for two reasons. First, we anticipate some (maybe up to 50%) of our participants will have already taken up the vaccine by the time this survey is approved to conduct. Therefore the number of participants available for our primary analysis described in section 5 may only be 100. Second, 100 is still more than Kidwell's study 1, and this may allow us to detect smaller differences between groups. If the results of this pilot study support a full study, we will seek ethical approval for that full study and include in our application a sample size calculation informed by the effect size found in this study.

Rationale/Strategy: The sampling strategy is a sample of convenience of Prolific Academic UK panellists. Recruitment will be stratified using the Prolific's "Political Party Affiliation UK" pre-screening question, such that 100 opportunities to take part will be made available to panellists who identify with the Labour party and the remaining 100 opportunities to panellists who identify with the Conservative party.

To be clear, participants will not be asked what party they affiliate with in our survey, rather participants have already indicated which party they affiliate with in their Prolific Academic profile.

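### Nothing asked before the appeal separates vaccine-inclined from vaccine-averse people in the primary analysis set; one factual question on last season, used as a covariate with age, would cheaply improve precision

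*Protocol*

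**What the plan says.** Protocol Section 5.3 sets out the survey in order and says that every part is described. Before the appeal it collects demographics (age, region, gender, ethnicity), the 10-item conservatism scale, self-rated political orientation, and current-season vaccination status: "Next participants will be asked whether they received an influenza vaccination in the 20/21 season already (Yes or No". Those who answer no are randomised to one of two appeals. Intention to have the influenza vaccine, the free-text reason, and the COVID-19 vaccine and mask intentions all come after the appeal.

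Section 5.4 states: "The primary analysis will only include those participants who have not yet vaccinated". The primary model is a multiple regression in which "Political ideology (continuous variable), Appeal type (nominal variable) and the interaction between Political ideology and Appeal type will be used to predict vaccination intentions". Age, gender, ethnicity and region are used only for description and for comparing the randomised groups.

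On size, Section 6.1 says "The proposed sample size is 200", that "we anticipate some (maybe up to 50%) of our participants will have already taken up the vaccine", and that therefore "the number of participants available for our primary analysis described in section 5 may only be 100". It adds that the effect size found here will inform the sample size of a full study.

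**The concern.** The only vaccine question asked before randomisation defines the primary analysis set, so it takes the same value for everyone in it and cannot serve as a covariate. Yet the people in that set probably differ in standing willingness to vaccinate. Section 3 says that free vaccination for people aged 50 and over comes only later in the season, so the not-yet-vaccinated plausibly include some who are waiting and some who decline. The part of that difference that does not follow ideology ends up in the residual of the interaction test.

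What is at stake is the width of the interval around the interaction and the power to detect it. Both matter here because the set is small, the target is an interaction, and the estimate is to be carried into the next sample size calculation.

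This cannot be left to a later analysis plan. The survey is anonymous and answered once, and no contact details are taken. An item that is not asked cannot be recovered.

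**Working it through.** **Inputs from the protocol.** Planned total 200 and up to 50% already vaccinated (Section 6.1); three model terms and a 5% significance level (Section 5.4).

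**Assumed, because the protocol gives no figure.** Two-sided test; 1:1 allocation; the share R2 of residual variance in intention that a prior-season item explains; its prevalence (30% taken); the difference in intention between its two groups, in SD units; and a starting power of 60%, chosen only to illustrate.

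**1. The plan's own figure.** 200 × (1 − 0.50) = 100. It reproduces.

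**2. What the unadjusted test can detect.** A noncentral F test of one coefficient was used, with 1 numerator df, noncentrality f2 × n and n = 100. Power of 80% needs f2 of about 0.080, a partial correlation of √(0.080/1.080) ≈ 0.27.

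**3. How much a yes/no item could explain.** With prevalence q and a difference of D SD, R2 = q(1−q)D² / [1 + q(1−q)D²].
- D = 0.5: 0.3 × 0.7 × 0.25 = 0.0525; R2 = 0.0525/1.0525 = 0.05.
- D = 1: 0.3 × 0.7 × 1 = 0.21; R2 = 0.21/1.21 = 0.17.

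**4. What that buys.** The standard error is multiplied by √(1 − R2), equivalent N is 100/(1 − R2), and f2 becomes f2/(1 − R2). The f2 that gives 60% power unadjusted is about 0.050.

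| R2 | SE multiplier | Equivalent N | Power (60% unadjusted) |
|---|---|---|---|
| 0.05 | 0.975 | 105 | 62% |
| 0.10 | 0.949 | 111 | 65% |
| 0.17 | 0.911 | 120 | 68% |
| 0.20 | 0.894 | 125 | 70% |
| 0.30 | 0.837 | 143 | 75% |
| 0.40 | 0.775 | 167 | 82% |

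On the assumptions in step 3, the rows for 0.05 to 0.17 are the relevant ones. R2 of about 0.32 would need a difference of 1.5 SD at 30% prevalence, and nothing in the protocol supports so large a difference. Spending two or three degrees of freedom instead of one leaves these powers unchanged to the nearest percentage point.

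**5. Validity of the plan as written.** In simulation (4,000 runs per scenario, n = 100, covariate independent of ideology), the unadjusted interaction estimate was unbiased and its type I error was about 5%. With R2 = 0.20 and a true interaction of 0.2, the empirical standard error fell from 0.103 to 0.092 on adjustment, and power rose from 49% to 57%. With R2 = 0, adjustment changed power from 48.4% to 48.0%, so a useless covariate costs almost nothing.

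**The case against.** The strongest reply is that nothing here is an error. A randomised comparison without a prognostic covariate is valid, and this is a declared pilot. That stands, and it is why the point is offered only as an improvement.

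The item also suits this population imperfectly. Section 3 says that free vaccination below age 65 is new this year, so a no for 2019/20 from someone aged 50 to 64 may reflect access and not unwillingness. This also stands: it would weaken the item as a predictor, and it is the reason to enter age alongside it. Age is already collected and could be added in any case, but it does not tell a 55-year-old who is waiting from one who refuses.

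A question about past vaccination might prime answers. The possibility is small: it asks for a fact and not for the outcome, and it would stand next to a factual vaccination question already asked.

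A main effect may not be enough. If prior vaccination is related to ideology and also changes the response to the appeal, a main-effect adjustment does not take that out of the ideology-by-appeal term. This stands, and calls for a sensitivity analysis.

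Finally, the full survey is an attachment that was not available, so the absence of such an item is inferred from the description in Section 5.3.

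**Conclusion.** A cheap improvement in precision. The primary set has no pre-appeal measure of vaccine inclination that varies within it, and the primary model has no prognostic covariate. On the assumed inputs, one yes/no item makes 100 participants worth about 105 to 120. Larger gains are possible but have no support in the documents.

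A reader might infer three stronger things, none of which is supported:
- That the primary analysis is biased or its error rate wrong. The simulation shows neither when the item is independent of ideology.
- That unmeasured inclination is the largest source of outcome variance, or that all of it falls into the residual. The protocol gives no variance figures, and the ideology main effect absorbs whatever part follows ideology.
- That one question would remove the problem. A single binary item captures only part of willingness to vaccinate.

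**What to change.** Before the appeal, next to the 2020/21 question, ask everyone: *Did you have an influenza vaccination last season (2019/20)? Yes / No / Not sure.* Pre-specify the answer as a main-effect covariate in the primary regression, together with age, which is already collected. Keep the ideology-by-appeal interaction as the primary test. Add a prior-vaccination-by-appeal term as a sensitivity analysis.

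The cost is a few seconds in an 8-minute survey, a minor change to the survey file under ethics review, one or two degrees of freedom for the item and one for age, and a small possibility of priming. No extra participants are needed. The change has to be made before the survey opens.
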